13.3.35 Incomplete dates for last known date patient alive or death

All dates must be completed with day, month and year. If the day is missing, the 15th of the month will be used for incomplete death dates or dates of last contact.

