10.4.2 Secondary efficacy endpoints

Overall survival

Overall Survival (OS) is defined as the time from the date of start of treatment to the date of death due to any cause. The survival time for patients without documentation of death prior to the data cutoff, will be censored at the last date the patient was known to be alive prior to the cutoff date. Survival time for patients with no post-baseline survival information will be censored at the date of start of treatment. OS will be analyzed using the Kaplan Meier method. Survival rate at 4, 6, 8, 12, 18 and 24 months and median OS will be estimated along with 95% confidence intervals from the Kaplan Meier distribution. The FAS will be used.

Progression Free Survival

Progression free survival (PFS) is defined as the date of the start of treatment to the date of the event defined as the first documented progression or death due to any cause. If patient has not had an event, progression-free-survival is censored at the date of last adequate tumor assessment. Kaplan-Meier analysis of PFS will be conducted for each cohort.

Best Overall Response and Disease Control Rate.

Overall lesion assessments will be listed by patient. Best overall response (BOR) will be summarized for the each cohorts using the Overall Response Rate and the Disease Control Rate which are the proportion of patients having respectively a best overall response of PR or CR, or SD, PR or CR. The estimated ORR and corresponding 90% confidence intervals based on the binomial distribution will be reported.

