- Date of last contact is defined as the last date the patient was known to be alive. This corresponds to the latest date for either the visit date, lab sample date or tumor assessment date. If available, the last known date patient alive from the survival follow-up page is used. If no survival follow-up is available, the date of discontinuation is used as last contact date.
- Date of secondary anti-cancer therapy is defined as the start date of any additional (secondary) antineoplastic therapy or surgery.

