13.3.33 Calculation of 'time to event' variables

Time to event = end date - start date + 1 (in days)

When no post-baseline tumor assessments are available, the date of randomization/start of treatment will be used as end date (duration = 1 day) when time is to be censored at last tumor assessment, i.e. time to event variables can never be negative.

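### Setting a missing day of death or last contact to the 15th has no lower bound, so it can give a negative OS or PFS time or a date before the patient was last seen alive

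*Combined protocol and SAP*

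**What the plan says.** Section 13.3.35 first asks for full dates: "All dates must be completed with day, month and year". It then gives the fallback: "If the day is missing, the 15th of the month will be used for incomplete death dates or dates of last contact". It does not tie the imputed day to the first dose or to any later date on which the patient was known to be alive.

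Section 13.3.33 computes every time-to-event variable in days as end date minus start date plus 1. For a patient with no post-baseline tumor assessment, "the date of randomization/start of treatment will be used as end date (duration = 1 day) when time is to be censored at last tumor assessment". The sentence closes by stating that "time to event variables can never be negative".

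Section 10.4.2 counts OS from start of treatment to death from any cause, and PFS from start of treatment to first documented progression or death. A patient not known to have died is, for OS, "censored at the last date the patient was known to be alive prior to the cutoff date".

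Section 13.3.24 defines last contact as the last date known alive, taken as the latest visit, laboratory or tumor assessment date. It then adds: "If available, the last known date patient alive from the survival follow-up page is used". No comparison with a later visit or sample is described.

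**The concern.** An imputation rule for partial dates should never contradict a complete date already in the database. This one can, in three ways:

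- **Before first dose.** A death in the month treatment began can be placed before treatment, giving a time that 13.3.33 says is impossible.
- **Before a later visit or scan.** A death can be placed before a visit at which the patient was alive. If that visit's scan showed progression, the PFS event becomes a death dated ahead of the progression.
- **Before a later complete contact.** A month-only entry on the survival page becomes the 15th and, read literally, takes precedence over a complete visit or laboratory date later in the same month. OS is then censored too early.

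The first case concerns the earliest deaths. Cohorts 2 and 3 have 10 patients each, so one mishandled record is visible in a Kaplan-Meier estimate.

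**Working it through.** **Inputs.** The time formula and the 1-day floor come from 13.3.33, the 15th-of-month rule from 13.3.35, and the start and event definitions from 10.4.2. The documents do not say how often the day is missing.

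**The plan's own figure.** With the end date set to the start date, end - start + 1 = 0 + 1 = 1 day, as 13.3.33 states.

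**Death in the month of first dose, day missing.** For a first dose on day s, time = 15 - s + 1 = 16 - s.

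| First dose on day | Time (days) |
|---|---|
| 15 | 1 |
| 16 | 0 |
| 17 | -1 |
| 20 | -4 |
| 25 | -9 |
| 31 | -15 |

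The result is negative from day 17 on. Day 16 gives 0, which is not negative but is below the 1-day minimum. A negative result requires a first dose between the 17th and the 31st and a death in the same month, so the death is at most 31 - 17 = 14 days after first dose.

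**Does another rule catch this?** The floor in 13.3.33 applies when time is censored at the last tumor assessment. It does not reach OS, or PFS when the event is a death. Section 10.4.2 censors at treatment start when there is no post-baseline survival information, but a recorded death with a partial date is such information. No other section bounds the imputed day.

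**How often, given a missing day.** I enumerated every start date in a four-year calendar (1,461 days), assuming start dates and death times are uniform.

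| Death after first dose (days) | Share with negative time |
|---|---|
| 0-7 | 36% |
| 0-14 | 24% |
| 0-28 | 13% |

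These are shares of deaths with a missing day, not of all deaths.

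**Death dated before a documented visit.** Take a visit on 25 March and a death recorded only as March. The imputed death is 25 - 15 = 10 days before the patient was seen alive. On the same calendar, the imputed death precedes the visit in these shares of cases:

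| Days from visit to true death | Share |
|---|---|
| 1 | 47% |
| 7 | 28% |
| 14 | 5% |
| 20 or more | 0% |

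**Size of the date error.** The imputed day is at most 15 - 1 = 14 days late and at most 31 - 15 = 16 days early. The average error over the calendar is under one day, so median OS and PFS would barely move.

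**The case against.** The strongest reply is that the damaging case is narrow and the data most likely to be complete are the ones at issue. A death within 14 days of first dose is also within 30 days of last dose, so it is a serious adverse event (8.2.1), notified within 24 hours and fully reported within 3 business days (8.2.2.2). Full dates are required, and missing values are queried (9.4). The four-monthly survival contacts that make month-only dates plausible come after treatment stops. This stands as an argument about frequency. It does not repair the rule: 13.3.24 takes the death date from the treatment completion, study evaluation completion or survival pages, and no reconciliation with the safety report is described.

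A second reply is that 13.3.27 calls this material guidance and 13.3.37 expects programs to be adapted. But 13.3.32 directs that these rules be used for programming efficacy results, and nothing in the combined document supplies the missing bound.

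A third reply is that the non-negativity clause only explains the tumor-assessment rule before it. That is a fair reading of its origin, but its wording covers time-to-event variables generally, and a negative survival time is impossible in any case. Similarly, the opening definition of last contact in 13.3.24 supports using a later visit. The survival-page sentence that follows leaves this unclear.

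Three stronger inferences are not supported:

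- **Early deaths in general get negative times.** The day must be missing, the first dose must be on the 17th or later, and death must fall in the same month.
- **Software will drop the negative times and inflate survival.** The documents say nothing of the kind, and a death at -4 days entered in the Python package statsmodels was kept as an event. If a cleaning step did remove one death from a cohort of 10, the 4-month OS estimate would rise by 10 points if it were the only death by then (9/10 to 9/9), or by 5.6 points with five deaths (5/10 to 5/9).
- **A cut-off early in a month lets the 15th become a censoring date after the cut-off.** Section 10.4.2 already confines OS censoring to dates before the cut-off.

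**Conclusion.** The point holds as a real but small internal contradiction. Followed literally, 13.3.35 produces zero or negative OS or PFS times that 13.3.33 excludes. It can also place deaths or last contacts before dated evidence that the patient was alive. This is a stated rule giving an impossible result, not merely an omitted detail.

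The likely effect on the results is slight. OS and PFS are secondary and descriptive, individual dates shift by about two weeks at most, and the ORR analysis and the Cohort 1 decision rule do not use these dates. The percentages above rest on uniform dates and apply only when the day is missing, which the documents do not quantify. The reason to act is that the correction is almost free and is better written down before any partial date is seen.

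**What to change.** Amend 13.3.35 so that, when the day is missing:

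- **Death or last contact:** use the later of the 15th and the last dated evidence that the patient was alive (first dose, visit, laboratory sample or scan). Keep the result within the recorded month and, for censoring dates, no later than the data cut-off.
- **Conflict:** if the dated evidence falls after the recorded month, query the site instead of imputing.
- **Last contact in 13.3.24:** use the latest of the imputed survival-page date and any complete contact date. This matches 13.3.34, which already ignores incomplete scan dates when complete ones exist.

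The bound should be the last date alive itself, not the day after. The day after 31 March would move a March death into April.

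With this rule, a first dose on 20 March and a death recorded as March gives 20 - 20 + 1 = 1 day. The minimum is 1 day for every start date in the four-year calendar, in agreement with 13.3.33. In the 25 March example, the death is dated 25 March and no longer precedes the scan.

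The cost is a few sentences in 13.3.35 and 13.3.24 and a few lines of programming. No new data are needed.

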13.3.36 Non-target lesion response

If no non-target lesions are identified at baseline (and therefore not followed throughout the study), the non-target lesion response at each assessment will be considered 'not applicable (NA)'.

13.3.37 Study/project specific programming

The standard analysis programs need to be adapted for each study/project.

13.3.38 Censoring reason

In order to summarize the various reasons for censoring, the following categories will be calculated for each time to event variable based on the treatment completion page, the study evaluation completion page and the survival page.

For survival the following censoring reasons are possible:

- Alive
- Lost to follow-up

For PFS and TTP (and therefore duration of responses) the following censoring reasons are possible:

- Ongoing without event
- Lost to follow-up
- Withdraw consent
- Adequate assessment no longer available*

Event documented after two or more missing tumor assessments (optional, see

Table)

- Death due to reason other than underlying cancer (*only used for TTP and duration of response*)
- Initiation of new anti-cancer therapy

*Adequate assessment is defined in Section 13.3.24. This reason is applicable when adequate evaluations are missing for a specified period prior to data cut-off (or prior to any other censoring reason) corresponding to the unavailability of two or more planned tumor assessments prior to the cut-off date. The following clarifications concerning this reason should also be noted:

- This may be when there has been a definite decision to stop evaluation (e.g. reason="Sponsor decision" on study evaluation completion page), when patients are not followed for progression after treatment completion or when only UNK assessments are available just prior to data cut-off).
- The reason "Adequate assessment no longer available" also prevails in situations when another censoring reason (e.g. withdrawal of consent, loss to follow-up or alternative anticancer therapy) has occurred more than the specified period following the last adequate assessment.
- This reason will also be used to censor in case of no baseline assessment.

13.4 Appendix 4: COVID-19 Precautions

Due to the emerging pandemic for *SARS-CoV-2* virus, it has become necessary to enact social distancing and limit hospital and outpatient facility interactions and visits for vulnerable patient populations. Patients receiving active therapy to control their metastatic cancer are particularly vulnerable.

This study involves patients receiving an oral targeted therapy that can either control cancer growth (stable disease) and shrink cancer disease (partial or complete responses), thereby prolonging life and maintaining quality of life. It is vital that these patients continue to receive these therapies, but also important that we mitigate the risk of virus transmission for patients, providers, and family members. In the coming weeks and months, as governments manage the *SARS-CoV-2* virus pandemic, it is quite possible that travel between states and cities may be limited, or that cities may have curfews. This amendment seeks to mitigate risk and enable ongoing care as feasible.

This appendix proposes the following changes for this investigator-initiated trial:

- Convert whenever possible all outpatient office visits to tele-medicine (video and phone) as necessary to continue monitoring, care, and treatment. Patients with concerning symptoms or labs from tele-medicine visits may be escalated to in-person evaluations as needed in the appropriate setting. This will serve to triage patients based on needs versus risk.
 - For example, some patients on this study may be on a well-tolerated and effective therapy dose for 6 to 30 months, and have little need to be seen in-person in the clinic if there are no changes or new issues.
- Patients will continue to have necessary blood work and scans to monitor for toxicities and disease status. Basic study procedures such as blood draws, radiographic scans, ECHO, ECG can be done by patients' local providers. These results will be reviewed by the Study Team centrally.
- ECHO and ECGs are for data collection, but are not expected to find rare abnormalities. These can be deferred unless prompted by symptoms or clinical concern.
- We will provide the option for oral therapies to be shipped to patients from our Investigational Drug Pharmacy or patients/family members could pick them up.
